In a prospective randomized controlled clinical trial, Testori et al. (25) compared the histologic and histomorphometric vital bone formation and residual graft volume in human bilateral sinus augmentations performed with either large (1.0 to 2.0 mm) or small (0.25 to 1 mm) particle size anorganic bovine bone matrix in 13 patients. For each patient, one subantral compartment was grafted with 100% large particle Bio-Oss and the contralateral subantral compartment was grafted with small particle Bio-Oss. At stage-one implant placement surgery 24 to 32 weeks later, a trephine core sample was taken (10 × 3 mm) from the superior-distal area of the former lateral window site as identified by measurements taken at the time of sinus elevation. Blinded paired histomorphometric and histologic analysis was subsequently performed on 11 bilateral cases. Vital bone formation was 26.77% ± 9.63% vs 18.77% ± 4.74% for the large particle and small particle grafts, respectively. Residual xenograft was 20.01% ± 8.97% vs 21.66% ± 10.47% for the large and small particle grafts, respectively. At the 24- to 32-week time interval, the new bone appeared as woven bone with several large rounded osteocyte lacunae. Close contact between graft granules embedded in the mineralized bone and bone matrix is observed. Hence, the histologic results of this study reaffirm the osteoconductive ability of the ABBM (Bio-Oss) when used as the sole grafting material in maxillary sinus augmentation and the histomorphometric results indicate a statistically significant increase in vital bone formation when the larger particle size is used. These findings were not shown in a previous maxillary sinus augmentation study where there was not a statistically significant difference in the percentage of new vital bone formation. (26) The authors related the difference between studies to the small sample size included in both. (25)

3. Objectives/Specific Aims:

The aim of this study is to histologically and clinically compare the amount of the bone gained after lateral ridge augmentation (edentulous ridge) procedures performed using small versus large particle size bone cortico-cancellous allograft (Maxxeus™ Dental, Community Tissue Services, Kettering, OH).

[figure not shown]

Fig. 3. Maxxeus Allograft ;
(A) Small particles (100-300µm). (B) Large particles (1000-2000µm).

Histomorphometric outcomes(Primary Outcomes):

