- evaluate the quality of bone regenerated with the use of the two available bone allograft particle sizes
- evaluate whether the size of commercially available bone allografts influences the outcomes of guided bone regeneration (GBR) procedures

Clinical and Radiographic outcomes(Secondary Outcomes):

- quantify the amount of bone augmentation achieved by the two available bone allograft particle sizes by direct clinical measurements
- quantify the amount of bone augmentation achieved by the two available bone allograft particle sizes by radiographic measurements (CBCT)
- evaluate the handling characteristics of the two available bone allograft particle sizes.

4. Materials and Method:

Study population

A total of 50 patients seeking treatment at the UAB SOD Graduate Periodontology clinics will be recruited to participate in this study according to the criteria in Table 1.

If deemed eligible, study visits, objectives, risks and benefits will be explained to all participants and IRB-approved written informed consent will be obtained.. One trained calibrated examiner will be available for all study visits when clinical measurements are required. Photographs will be taken during all visits using a SLR digital camera in a 1:1 ratio.

Randomization

Randomization will take place on the day of surgery via sealed envelopes indicating the surgical approach the patient will receive, as follows:

- Group 1: Small particle (SP) bone allograft (0.25-1.0 mm), or
- Group 2: Large particle (LP) bone allograft (1.0-2.0 mm)

Table 1. Study Inclusion and Exclusion Criteria

Inclusion Criteria	Exclusion Criteria
Patients:  English speaking  At least 18 years old  Able to read and understand informed consent document  Need implants to replace missing tooth or teeth in at least one quadrant of the mouth.  Patient at UAB dental school  willing and able to comply with the preoperative and postoperative diagnostic and clinical evaluations required.	
• Systemic conditions contraindicating oral surgical procedures or adversely affecting wound healing• significant medical conditions or habits expected to interfere with bony healing.
	Smoking >10 cigarettes/day
	Patient is a poor compliance risk (i.e., poor oral hygiene, history of alcohol or drug abuse)

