The sutures will be removed after two weeks after cleaning the sutures with a gauze stacked with Peridex® chlorhexidine mouth rinse . Surgical sites will be evaluated for healing status and postoperative instructions on resuming oral hygiene measures will be instructed to patients.

Visit 3 (Bone Biopsy and Implant Placement):

Six months post-ridge augmentation, a second CBCT scan will be taken to evaluate the success of the grafting procedures and to plan the optimal implant position. The sites will be exposed for surgical placement of implants. The surgical approach will be similar to the

procedures for the graft procedures. After exposure of the bone the implant sites will be located with the use of the surgical stent (prepared by the restoring dentist) and the ridge width will be measured at the crest and 4 mm apical to the crest with the same standardized caliper. If ridge width permits implant placement, root form dental implants will be placed. Prior to implant placement a bone biopsy will be taken from the implant sites using a 2 mm internal diameter trephine (Fig. 6). For the bone biopsy, first the new bone will be measured, next the center of the new bone will be identified, and finally the core will be taken from the center of the new bone. The biopsy will be stored in the correct medium and will be sent to the Histomorphometry and Molecular Analysis Core for histomorphometric analysis. The implant preparation will be completed and implants will be placed according to manufacturer protocol.

[figure not shown]

Fig.6 Bone Biopsy taken prior to implant placement using a trephine

All clinical measurements will be taken by one experienced examiner blinded to the randomization process (small vs. large particles) before grafting and at time of implant placement. Another examiner will perform the radiographic evaluations and will also be blinded to the randomization process. Intra-examiner calibration will be conducted to ensure reliability of measuring method.

Sample size rationale:

To reject the null hypothesis of equal means with a significance level (alpha) of 0.05 using a two-sided two-sample unequal-variance t-test, 22 patients in each group (total of 44) will reach 0.90 statistical power. Accounting for a 8 patient loss-to-follow up, 50 patients will be enrolled in the study.

Histomorphometric Analysis

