Using baseline and implant placement CBCT data, the 2 scans will be superimposed in a virtual implant planning software (coDiagnostix) to evaluate 3-D volumetric changes (in cc). In addition, a virtual tooth (planned in optimal position at the implant site) will serve as reference point for standardized assessment of 2-dimensional ridge width and height changes (in mm) from the time of grafting until time of implant placement.

Statistical Analysis

To reject the null hypothesis of equal means with a significance level (alpha) of 0.05 using a two-sided two-sample unequal-variance t-test, 22 patients in each group (total of 44) will be required to reach 0.90 statistical power. Accounting for 8-patient loss-to-follow up, 50 patients will be enrolled in the study.

A two-sample t-test was conducted to compare the difference between the two groups in terms of new bone formation. Both the clinical and the radiographic dimensional changes between the groups were evaluated using two-sample t-tests. A paired t-test was used to compare among all subjects the radiographic vertical loss at the facial, midline, and lingual of the crest. The correlation between the clinical and radiographic changes in width at the crest and the influence of the type of tooth site on the radiographic dimensional changes were evaluated with two-sample t-tests.

References

1. Cardaropoli, G., M. Araujo, and J. Lindhe, Dynamics of bone tissue formation in tooth extraction sites. An experimental study in dogs. *J Clin Periodontol*, 2003. **30**(9): p. 809-18.
2. Araujo, M.G. and J. Lindhe, Dimensional ridge alterations following tooth extraction. An experimental study in the dog. *J Clin Periodontol*, 2005. **32**(2): p. 212-8.
3. Nevins, M., et al., A study of the fate of the buccal wall of extraction sockets of teeth with prominent roots. *Int J Periodontics Restorative Dent*, 2006. **26**(1): p. 19-29.
4. Tan, W.L., et al., A systematic review of post-extraction alveolar hard and soft tissue dimensional changes in humans. *Clin Oral Implants Res*, 2012. **23 Suppl 5**: p. 1-21.
5. Jambhekar, S., F. Kern, and A.S. Bidra, Clinical and histologic outcomes of socket grafting after flapless tooth extraction: a systematic review of randomized controlled clinical trials. *J Prosthet Dent*, 2015. **113**(5): p. 371-82.

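### The enrolment sum does not close: 44 required patients plus 8 allowed losses is 52, not 50, so enrolling 50 covers only 6 losses

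*Combined protocol and SAP*

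**What the plan says.** The extraction-socket protocol gives its sample size twice, in section 4 (Materials and Methods) and again under Statistical Analysis. Both places say that "22 patients in each group (total of 44) will be required to reach 0.90 statistical power", and both continue: "Accounting for 8-patient loss-to-follow up, 50 patients will be enrolled in the study".

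The ridge protocol, under Sample size rationale, gives the same figures: "22 patients in each group (total of 44) will reach 0.90 statistical power", followed by "Accounting for a 8 patient loss-to-follow up, 50 patients will be enrolled in the study". Its Study population paragraph repeats the total: "A total of 50 patients seeking treatment at the UAB SOD Graduate Periodontology clinics will be recruited to participate in this study".

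The stated basis in all three statements is a "significance level (alpha) of 0.05 using a two-sided two-sample unequal-variance t-test". No mean difference and no SD accompany any of them.

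**The concern.** The loss allowance is a count of patients, so required number plus losses should equal enrolment. It does not. If 8 patients are lost from 50, 42 remain, two below the 44 that the socket protocol calls required.

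This affects how the result is read. The primary outcome in both protocols comes from a bone core taken at implant placement, six months after grafting in the ridge protocol and three months in the socket protocol. A patient lost before that visit contributes no primary outcome. If a sub-study finishes with 42 or 43 evaluable patients, the plan supports two opposite statements: losses stayed within the allowance, and the required number was not reached.

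**Working it through.** **Inputs from the plan.** Required n = 44 (22 per group); losses = 8; enrolment = 50; two-sided alpha 0.05; unequal-variance (Welch) t-test; power 0.90. The socket protocol's permuted blocks aim at equal group sizes.

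**Step 1: the stated enrolment.**
- Required plus losses: 44 + 8 = 52, not 50.
- Enrolled minus losses: 50 − 8 = 42, or 21 per group if losses are balanced.
- Losses that 50 can absorb: 50 − 44 = 6, which is 6/50 = 12%.

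**Step 2: other readings of the 8.**
- As 8%: 44/(1 − 0.08) = 47.8, or 44 × 1.08 = 47.5; both round up to 48.
- As the proportion 8/52: 44/(1 − 8/52) = 52.
- As the proportion 8/50: 44/(1 − 0.16) = 52.4, rounded up to 53.

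None gives 50. A 12% loss does, since 44/0.88 = 50. So does 10% rounded up within each group, since 22/0.90 = 24.4, giving 25 per group. Neither is what the plan states.

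**Step 3: what 42 instead of 44 would cost.** The 22 per group cannot be reproduced without a mean difference and SDs, so the true power at 42 cannot be computed. It can be bounded. Welch power was taken from the noncentral t distribution with noncentrality

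δ = Δ / √(s₁²/n₁ + s₂²/n₂)

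and Satterthwaite degrees of freedom.

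- *If 22 per group is exactly the 0.90 size, equal SDs.* The implied standardized difference is 1.0005. At 22 per group, δ = 1.0005/√(2/22) = 3.318 and power is 0.900. At 21 per group, δ = 1.0005/√(2/21) = 3.242 and power is 0.886. A simulation of 400,000 trials gave 0.885.
- *Unequal SDs, same condition.* For SD ratios of 2, 3, 5 and 10, with 22 per group set to 0.900, power at 21 per group is 0.885 each time.
- *If 22 is only the smallest whole number reaching 0.90, equal SDs.* At a standardized difference of 1.0253, 21 per group itself reaches 0.900. So 22 is the minimum only for differences from 1.0005 up to 1.0253, and over that range 21 per group gives 0.886 to just under 0.90.

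**Step 4: an illustration on assumed inputs.** The only SDs the documents give for small versus large particles are in the background sections: "Vital bone formation was 26.77% ± 9.63% vs 18.77% ± 4.74% for the large particle and small particle grafts, respectively". The plan does not tie these to its calculation. They come from a within-patient xenograft study of sinus grafts, so using them for two parallel groups is an assumption. With Δ = 26.77 − 18.77 = 8.00 and SDs of 9.63 and 4.74:

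| Per group | Power |
|---|---|
| 20 | 0.895 |
| 21 | 0.910 |
| 22 | 0.923 |

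On these inputs the requirement would be 21 per group, and 42 + 8 = 50 would close. This does not show how the plan was derived, since the plan says 22. It shows only that the wrong figure could be the 44 as easily as the 8.

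**The case against.** The arithmetic itself is not open to dispute; the objections concern scope and weight.

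- **The gap is two patients.** A difference that small would usually pass as rounding in a sample-size calculation. Here, though, three stated whole numbers are being added, and there is no rounding or choice of formula to absorb it. What stands is that the consequence is small.
- **The wrong figure could be the 50.** If 44 and 8 are both right, enrolment should read 52. That reading is logically open. It is not needed to remove the contradiction, because the allowance can be restated without recruiting anyone.
- **Some of this may already be history.** The socket protocol's Statistical Analysis section describes its tests in the past tense, while the ridge protocol is written in the future tense. If the socket data are analysed, restating its design as 42 evaluable is proper only if the original calculation supports it. That is a fair constraint on the fix.
- **Losses need not be balanced.** If all 8 fell in one group (25 versus 17), power with equal SDs would be about 0.871. With an SD ratio of 2 it would be about 0.827 if they fell in the more variable group and about 0.91 if in the other. These are extremes: under random loss from two groups of 25, the chance that all 8 come from one group is about 0.4%.
- **The sinus figures are not the plan's inputs.** Correct; they serve only as an illustration, and the conclusion does not depend on them.
- **The missing mean difference and SDs are a separate and larger gap.** Agreed. They matter here only because their absence stops a reader from finding which figure is wrong.

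**Conclusion.** The concern holds. All three sample-size statements contradict themselves, and no other passage resolves them. At least one of 44, 8 and 50 is wrong, and the documents do not show which.

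The size is two patients, or one per group if losses are balanced. In that case the power shortfall at 42 evaluable lies between nil and about 1.5 percentage points (0.900 − 0.885). The upper end assumes that 22 per group is exactly the 0.90 size; the lower end applies if 21 per group already reaches 0.90. Severe imbalance in losses could cost more but is improbable. This is a minor error of statement, not a threat to the trial's ability to answer its question.

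**What to change.** Retrieve the original calculation and correct the wrong figure in all three places: the ridge protocol's Sample size rationale, and the socket protocol's section 4 and Statistical Analysis. Two corrections close the sum without recruiting anyone:

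- **(a) 44 and 50 stand.** State that 50 allows for 6 losses (12%, 3 per group).
- **(b) 8 and 50 stand.** Restate the design as 42 evaluable (21 per group), with power recomputed from the mean difference and SDs actually used. The value 0.886 should not be quoted without those inputs, because it applies only if 22 per group is exactly the 0.90 size.

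In either case, add one sentence giving the mean difference and SDs. Where data have already been analysed, make the change as a dated clarification, and use (b) only if the original calculation supports 21 per group.

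The cost is one figure and one sentence in three places. The stated loss allowance under (a), or possibly the stated power under (b), becomes slightly less favourable. No extra patients, visits or analyses are needed.

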The use of large sized particles of anorganic bovine bone matrix resulted in significantly more vital bone formation than small particle grafts ($26.77\% \pm 9.63\%$ vs $18.77\% \pm 4.74\%$, respectively) in a prospective randomized controlled clinical trial of bilateral sinus augmentations [22]. While the histomorphometric results of this study indicated a statistically significant increase in vital bone formation when the larger particle size was used, these findings were not shown in a previous maxillary sinus augmentation study where there was not a statistically significant difference in the percentage of new vital bone formation [23]. The authors related the difference between studies to the small sample size included in both (<15 patients). Due to the conflicting information and paucity of the literature on this topic, this proposed study will help shed the light on the influence of bone graft particle size on the amount of new bone formation in the most common bone defect in the oral cavity, i.e. the extraction socket, after ridge preservation.

3. Objectives/Specific Aims

The aim of the study is to clinically and histologically analyze the amount of the bone gained after ridge preservation procedures performed using small (250-1000 μ m) versus large (1000-2000 μ m) particle size bone cortico-cancellous allograft (Maxxeus™ Dental, Community Tissue Services, Kettering, OH) at time of implant placement, 3 months following surgical intervention.

Specific objectives include:

- A. To compare the bone quantity (bucco-lingual ridge width) between the two bone allograft particle sizes by direct clinical measurements
- B. To compare the bone quantity (bucco-lingual ridge width and apico-coronal ridge height) between the two bone allograft particle sizes by 3-dimensional radiographic measurements (CBCT scan)
- C. To evaluate the quality of bone regenerated with the use of the two bone allograft particle sizes via histological and histomorphometric analyses.

Primary outcome: histologic and histomorphometric bone core analyses (from the implant preparation site).

Secondary outcomes: clinical and radiographic dimensional changes of the edentulous ridges.

Null Hypothesis: Large-sized particle bone allografts will achieve similar histologic and clinical outcomes as small-sized particle allografts.

4. Materials and Methods

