Patients presenting to the graduate periodontal clinic at the University of Alabama at Birmingham School of Dentistry will be screened according to the following criteria:

Inclusion criteria

- English speaking, able to read and understand informed consent document
- Hopeless non-molar tooth or teeth that are planned to be replaced with dental implants after ridge preservation
- Socket with residual 4 walls following minimally invasive tooth extraction (a dehiscence \leq 3 mm may be included)
- Healthy adjacent teeth must be present and not planned for extraction

Exclusion criteria

- Less than 18 years old
- Smokers/tobacco users (>10 cigarettes/day)
- Patients with systemic pathologies or conditions contraindicating oral surgical procedures or adverse affecting wound healing as uncontrolled diabetes
- Poor compliance risk (i.e., poor oral hygiene, history of alcohol or drug abuse)

To reject the null hypothesis of equal means with a significance level (alpha) of 0.05 using a two-sided two-sample unequal-variance t-test, 22 patients in each group (total of 44) will be required to reach 0.90 statistical power. Accounting for 8-patient loss-to-follow up, 50 patients will be enrolled in the study.

All clinical measurements are being taken by one experienced examiner blinded to the randomization process (small vs. large particles) before grafting and at time of implant placement. Another examiner will perform the radiographic evaluations and will also be blinded to the randomization process. Intra-examiner calibration will be conducted to ensure reliability of measuring method.

Screening/baseline visit:

Patients' medical history and electronic records will be reviewed. A treatment plan will be developed by an interdisciplinary team consisting of a periodontist and a restoring dentist and respective residents. Study examiners will conduct clinical and radiographic exams to determine eligibility according to the above criteria. If deemed eligible, study visits and objectives will be explained to all participants and IRB approved written informed consent will be obtained.

Surgical visit - Study visit 1:

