Three months' post-socket grafting, a second CBCT scan will be taken to evaluate the success of the grafting procedures and to plan the optimal implant position. The site(s) will be exposed for surgical placement of the implant(s). After exposure of the healed edentulous ridge, the implant sites will be located with the use of the surgical stent (prepared by the restoring dentist) and the ridge width will be measured at the crest and 4 mm apical to the crest with the same standardized caliper. If ridge width is deemed adequate, a dental implant of appropriate size will be placed. Prior to implant placement a bone biopsy will be taken from the implant site using a 2-mm internal diameter trephine. The biopsy will be stored in formalin and sent to the UAB Histomorphometry and Molecular Analysis Core for histomorphometric analysis.

[figure not shown]

Fig 4. A. Site after 3 months of healing, B. Flap elevation, C. Core biopsy trephine, D. Implant placement, E. Flap replaced and sutured.

Histomorphometric Analysis

Each specimen will be fixated with 10% neutral buffered formalin for 48 hours prior to be dehydrated and embedded in methylmethacrylate. It will be ground sectioned at the center of the biopsy in its long axis into 50-70 micron-thick sections (Exakt Technologies, Inc., Oklahoma City, OK), and polished with 4000 grit sandpaper and Novus Polish to create a surface as smooth as possible. All sections will be stained with Goldner's Trichrome stain and imaged for quantification of bone formation. Histomorphometry will be done using the Bioquant® Image Analysis Software (R&M Biometrics, Nashville, TN) by measuring the total surface of vital bone, residual graft particles, organic matrix and artifact/air components.

Corresponding percentages will be calculated for each of these tissues and compared between small and large particle grafts for ridge preservation and augmentation separately. These experiments will be conducted at the UAB Histomorphometry and Molecular Analysis Core and all measurements made by an experienced blinded lab technician.

Clinical and Radiographic Measurements

Direct measurements (in mm) of the bucco-lingual ridge width will be taken following tooth extraction at the largest area of the socket orifice, using a UNC-15 periodontal probe. This measurement will be repeated at time of implant placement, 3 months after socket preservation.

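### Socket protocol: the clinical ridge-width change, a secondary outcome, is compared without adjusting for the pre-graft width that is already collected, a possible loss of precision

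*Combined protocol and SAP*

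**What the plan says.** All references are to the extraction-socket protocol.

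- **Objectives/Specific Aims.** Objective A is "To compare the bone quantity (bucco-lingual ridge width) between the two bone allograft particle sizes by direct clinical measurements". The rank is explicit: "Secondary outcomes: clinical and radiographic dimensional changes of the edentulous ridges". The primary outcome is the bone-core analysis.
- **Clinical and Radiographic Measurements.** The starting value is defined as follows: "Direct measurements (in mm) of the bucco-lingual ridge width will be taken following tooth extraction at the largest area of the socket orifice", with a UNC-15 probe. Then: "This measurement will be repeated at time of implant placement, 3 months after socket preservation".
- **Materials and Methods.** "All clinical measurements are being taken by one experienced examiner blinded to the randomization process (small vs. large particles) before grafting", and again at implant placement.
- **Statistical Analysis.** "Both the clinical and the radiographic dimensional changes between the groups were evaluated using two-sample t-tests". No covariate, regression or baseline adjustment appears there or anywhere else in the document.
- **Study visit 3.** The surgical narrative also describes a width taken at the crest and "4 mm apical to the crest with the same standardized caliper. If ridge width is deemed adequate". The socket protocol describes no earlier caliper measurement.
- **Surgical visit.** The CBCT that serves as the radiographic baseline is taken immediately after the socket has been grafted.

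**The concern.** A t-test on change fixes the coefficient of the pre-graft width at 1. If wide and narrow sockets tend to converge during healing, the true coefficient is below 1, and subtraction then carries more of the baseline variation into the outcome than it should. A linear model estimates the coefficient from the same data.

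The pre-graft width is a legitimate covariate because it precedes the graft and the examiner is blinded. At stake is the width of the interval for objective A in a study of about 22 patients per arm. Chance imbalance in pre-graft width is also handled less well by subtraction than by adjustment.

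**Working it through.** **The plan's own figure.** The plan states 22 per group for 0.90 power, with no difference, SD or endpoint attached, so it cannot be reproduced without assumptions. It contains no ridge-width input, and only the number 22 is used below.

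**Inputs.** n = 22 per arm (Statistical Analysis), one independent value per patient. The SDs and the pre-post correlation rho are assumed, because the documents give neither. Set the follow-up SD to 1 and the pre-graft SD to k. The slope of follow-up on pre-graft width is then rho/k.

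**Large-sample variances.**
- Change: 1 + k² − 2·rho·k
- Adjusted: 1 − rho²
- Ratio, adjusted to change: (1 − rho²) / [(1 − rho²) + (k − rho)²]

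The ratio never exceeds 1 and equals 1 only at rho = k, that is, at slope 1. With equal SDs (k = 1) it reduces to (1 + rho)/2.

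**Small-sample cost.** Estimating the slope inflates the variance on average by 1 + 1/(2n − 4) = 1 + 1/40 = 1.025. The interval is therefore wider by a factor of √1.025 = 1.012.

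**Results for k = 1.** The simulation used 40,000 runs and compared the mean 95% interval width of the adjusted model with that of the unequal-variance t-test on change.

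| rho | Var(change) | Var(adjusted) | Ratio | √ratio × 1.012 | Simulated width ratio | Narrower by |
|---|---|---|---|---|---|---|
| 0.3 | 1.40 | 0.91 | 0.65 | 0.816 | 0.815 | 18% |
| 0.5 | 1.00 | 0.75 | 0.75 | 0.877 | 0.876 | 12% |
| 0.7 | 0.60 | 0.51 | 0.85 | 0.933 | 0.932 | 7% |
| 0.9 | 0.20 | 0.19 | 0.95 | 0.987 | 0.986 | 1% |

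**Unequal SDs, simulated width ratios.**
- k = 0.8, at rho 0.3, 0.5, 0.7, 0.8, 0.9: 0.895, 0.956, 1.002, 1.012, 0.985. The worst value is at rho = k, where the slope is 1.
- k = 1.25, at rho 0.3, 0.5, 0.7, 0.9: 0.717, 0.765, 0.802, 0.789. The largest gain needs a slope of 0.3/1.25 = 0.24, for which the documents offer no support.

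**Validity.** Simulated type I error was 0.047 to 0.051 for both methods.

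**Attrition.** If 8 of the 50 enrolled are lost, 42 remain, or 21 per arm. The small-sample factor becomes √(1 + 1/38) = 1.013, so the ratios barely move.

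**The case against.** The strongest reply is that nothing here is an error. The t-test on change is unbiased, matches the stated outcome and already uses the baseline by subtraction. No power claim for ridge width is undermined. All of this stands, and it limits the point to a possible gain in precision.

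The second reply is that the size is wholly assumed. This also stands. Grafting is meant to maintain ridge dimensions, and one calibrated examiner takes the clinical measurements. Both hint, without proving it, at a high slope and so a small gain. The large-gain cells above should not be taken as expected values.

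A reader might go further and infer that the analysed follow-up width is undefined, or that a probe baseline is subtracted from a caliper follow-up. The documents do not support this. The measurement section defines the socket-orifice width and says that this same measurement is repeated. The caliper sentence belongs to the surgical narrative and leads into the decision on implant placement. The later phrase "The correlation between the clinical and radiographic changes in width at the crest" is compatible with a socket-orifice width. What remains is a loose end: visit 3 speaks of the same caliper where none has been introduced.

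A further limit concerns the remedy. The inclusion criteria and visits 1 and 3 allow more than one tooth, socket or site per patient, whereas the calculations assume one independent value each. A model that ignored this would not be sound.

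**Conclusion.** The point holds as a minor one. The planned comparison of clinical width change leaves a collected, blinded, pre-graft covariate unused except by subtraction. The consequence is a possibly wider interval for one secondary outcome. A reader might infer bias, an inflated error rate or harm to the main result. None of these follows: the test is valid with independent patients, and the primary bone-core outcome has no baseline to adjust for.

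The gain cannot be stated from the documents. The figures of 18% to 1% narrower rest on equal SDs, correlations of 0.3 to 0.9 and 22 independent patients per arm. The balance still favours adjustment, because the worst case is an interval about 1% wider.

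**What to change.** 1. State that the clinical width outcome is the repeated socket-orifice width, analysed by a linear model with arm and pre-graft width, reporting the adjusted arm difference with its 95% confidence interval. With pre-graft width in the model, follow-up width and change give the same arm difference, so the dimensional-change outcome is kept.
2. State the unit of analysis. For patients with more than one socket, use one value per patient (for example the mean over sockets, with the baseline averaged in the same way), or a model that allows for within-patient clustering.
3. Keep the radiographic outcomes as change. Their baseline scan follows grafting and could reflect the allocated material, so it is not a pre-treatment covariate.
4. Reconcile the caliper wording at visit 3 with the probe measurement.
5. The Statistical Analysis section is written in the past tense. If the analyses are complete, report the planned t-test as planned and label the adjusted model as post hoc.

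The cost is a few sentences of SAP wording and one degree of freedom. No new data are needed.
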